7.3.2 Criteria for Tumor Response Evaluation

Tumor response evaluation will be performed according to RECIST version 1.1 (see Appendix I) by using CT or MRI and other modalities at a 6-week interval starting from the first dose of trial treatment. In the case of symptoms suggesting progression, subjects should be evaluated by imaging thereafter for documentation and confirmation of the tumor responses.

Evaluation of lesions should be based on images obtained by either CT or MRI. The same method of assessment and the same technique should be used to characterize each identified and reported lesion at baseline and during the trial. If a chest X-ray indicates metastatic disease while the subject is enrolled in this trial, a CT of the chest is required for confirmation. All assessments should be provided by the same physician or radiologist if possible during the trial.

Evaluation criteria for possible combination of tumor responses (e.g., target lesion, nontarget lesion, new lesion, and overall response) are provided in Appendix I.

7.4 Assessment of Safety

The safety profile of the IMP will be assessed through the recording, reporting and analysis of baseline medical conditions, AEs, physical examination findings including vital signs and laboratory tests.

Comprehensive assessment of any apparent toxicity experienced by each subject will be performed from the time of giving informed consent and throughout the trial. The Investigator will report any AEs, whether observed by the Investigator or reported by the subject (see Section 7.4.1.2). The reporting period of AEs is described in Section 7.4.1.3.

7.4.1 Adverse Events

7.4.1.1 Adverse Event Definitions

Adverse Event

An AE is any untoward medical occurrence in a subject or clinical investigation subject administered a pharmaceutical product, regardless of causal relationship with this treatment. An AE can therefore be any unfavorable and unintended sign (including an abnormal laboratory finding), symptom, or disease temporally associated with the use of a medicinal product, whether or not considered related to the medicinal product.

For surgical or diagnostic procedures, the condition/illness leading to such a procedure is considered as the AE rather than the procedure itself.

The Investigator is required to grade the severity or toxicity of each AE. Investigators will reference the National Cancer Institute - CTCAE, version 4.03 (publication date: 14 June 2010), a descriptive terminology that can be used for AE reporting.

A general grading (severity/intensity; hereafter referred to as severity) scale is provided at the beginning of the above referenced document, and specific event grades are also provided.

If a particular AE's severity is not specifically graded by the guidance document, the Investigator is to use the general CTCAE definitions of Grade 1 through Grade 5 following his or her best medical judgment.

The 5 general grades are:

- Grade 1 or Mild.
- Grade 2 or Moderate.
- Grade 3 or Severe.
- Grade 4 or Life-threatening.
- Grade 5 or Death.

According to the Sponsor's convention, any clinical AE with severity of Grade 4 or 5 must also be reported as an SAE; however, a laboratory abnormality of Grade 4, such as anemia or neutropenia, is considered serious only if the condition meets one of the serious criteria described below.

If death occurs, the primary cause of death or event leading to death should be recorded and reported as an SAE. "Fatal" will be recorded as the outcome of this specific event and death will not be recorded as separate event. Only, if no cause of death can be reported (for example, sudden death, unexplained death), the death per se might then be reported as an SAE.

Document No. CCI
Object No.

Investigators must also systematically assess the causal relationship of AEs to the IMP/trial treatment (including any other non-IMPs, radiation therapy, etc.) using the following definitions. Decisive factors for the assessment of causal relationship of an AE to the IMP/trial treatments include, but may not be limited to, temporal relationship between the AE and the IMP/trial treatments, known side effects of IMP/trial treatments, medical history, concomitant medication, course of the underlying disease, trial procedures.

Unrelated: Not reasonably related to the IMP/trial treatments. The AE could not medically

(pharmacologically/clinically) be attributed to the IMP/trial treatments under study in this clinical trial protocol. A reasonable alternative explanation must be available.

Related: Reasonably related to the IMP/trial treatments. The AE could medically

(pharmacologically/clinically) be attributed to the IMP/trial treatments under study

in this clinical trial protocol.

Abnormal Laboratory Findings and Other Abnormal Investigational Findings

Abnormal laboratory findings (Grade 1-3) and other abnormal investigational findings (for example, on an ECG trace) should not be reported as AEs unless they are associated with clinical signs and symptoms, lead to treatment discontinuation or are considered otherwise medically important by the Investigator. If a laboratory abnormality fulfills these criteria, the identified medical condition (for example, anemia, increased ALT) must be reported as the AE rather than the abnormal value itself.

For abnormal laboratory findings, which are recorded as AE, follow up measures should be performed.

Serious Adverse Event

An SAE is any untoward medical occurrence that at any dose:

- Results in death.
- Is life-threatening. (Note: The term "life-threatening" refers to an event in which the subject is at risk of death at the time of the event, not an event that hypothetically might have caused death if it was more severe.)
- Requires inpatient hospitalization or prolongs an existing hospitalization.
- Results in persistent or significant disability or incapacity.
- Is a congenital anomaly or birth defect.
- Is otherwise considered to be medically important. (Note: Important medical events that may not result in death, be life-threatening, or require hospitalization may be considered as SAEs when, based upon appropriate medical judgment, they may jeopardize the subject or may require medical or surgical intervention to prevent one of the outcomes listed above.

China First-line Head and Neck Trial (CHANGE2)

Examples of such events include allergic bronchospasm requiring intensive treatment in an emergency room or at home, blood dyscrasias or convulsions that do not result in inpatient hospitalization, or the development of drug dependency or drug abuse.)

For the purposes of reporting, any suspected transmission of an infectious agent via an IMP is also considered an SAE and described in Section 7.4.1.4.

Events that Do Not Meet the Definition of an SAE

Elective hospitalizations to administer, or to simplify trial treatment or trial procedures (for example, an overnight stay to facilitate chemotherapy and related hydration treatment application) are not considered SAEs. However, all events leading to unplanned hospitalizations or unplanned prolongation of an elective hospitalization (for example, undesirable effects of any administered treatment) must be documented and reported as SAEs.

Events Not to Be Considered as AEs/SAEs

Medical conditions present at the initial trial visit that do not worsen in severity or frequency during the trial are defined as Baseline Medical Conditions, and are NOT to be considered AEs.

In this trial, PD is the only medically anticipated clinical event which is considered as a clinical efficacy outcome rather than an AE. No other medically anticipated events are defined in this trial as efficacy outcomes.

However, if adverse signs or symptoms occur in association with PD then these should be recorded as AEs.

AE/SAEs Observed in Association with Disease Progression

Disease progression recorded in the course of efficacy assessments only, but without any adverse signs or symptoms should not be reported as AEs.

However, if adverse signs and symptoms occur in association with disease (tumor) progression, such as dyspnea, tumor pain, bleeding etc., then these should be recorded as AEs or reported as SAEs, if they meet criteria for seriousness.

7.4.1.2 Methods of Recording and Assessing Adverse Events

At each trial visit, the subject will be queried on changes in his or her condition. During the reporting period, any unfavorable changes in the subject's condition will be recorded as AEs, whether reported by the subject or observed by the Investigator.

Complete, accurate and consistent data on all AEs experienced for the duration of the reporting period (defined below) will be reported on an ongoing basis in the appropriate section of the eCRF.

All SAEs must be additionally documented and reported using the appropriate Report Form as described in Section 7.4.1.4.

It is important that each AE report include a description of the event, its duration (onset and resolution dates [and times when it is important to assess the time of AE onset relative to the recorded treatment administration time]), its severity, its causal relationship with the trial treatment, any other potential causal factors, any treatment given or other action taken, including dose reduction or discontinuation of the IMP, and its outcome. In addition, serious cases should be identified and the appropriate seriousness criteria documented.

Specific guidance can be found in the eCRF Completion and Monitoring Conventions provided by the Sponsor.

7.4.1.3 Definition of the Adverse Event Reporting Period

The AE reporting period for safety surveillance begins when the subject is initially included in the trial (date of first signature of informed consent) and continues until the Safety Follow-up visit.

Any SAE assessed as related to cetuximab must be reported whenever it occurs, irrespective of the time elapsed since the last administration of cetuximab.

7.4.1.4 Procedure for Reporting Serious Adverse Events

Serious Adverse Events

In the event of any new SAE occurring during the reporting period, the Investigator must immediately (within a maximum of 24 hours after becoming aware of the event) inform the Sponsor or its designee in writing. All written reports should be transmitted using the SAE Report Form, which must be completed by the Investigator following specific completion instructions.

For each SAE, all relevant medical information should be documented on the SAE report form.

In exceptional circumstances, an SAE (or follow-up information) may be reported by telephone; in these cases, a written report must be sent immediately by fax or e-mail. Names, addresses, and telephone and fax numbers for SAE reporting will be included in the trial-specific SAE Report Form.

Relevant pages from the eCRF may be provided in parallel (for example, medical history, concomitant medications). Additional documents may be provided by the Investigator, if available (for example, laboratory results, hospital report, and autopsy report). In all cases, the information provided on the SAE Report Form must be consistent with the data about the event recorded in the eCRF.

The Investigator must respond to any request for follow-up information (for example, additional information, outcome, final evaluation, other records where needed) or to any question the

China First-line Head and Neck Trial (CHANGE2)

Sponsor/designee may have on the AE within the same timelines as those noted above for initial reports. This is necessary to ensure prompt assessment of the event by the Sponsor or designee and (as applicable) to allow the Sponsor to meet strict regulatory timelines associated with expedited safety reporting obligations.

Requests for follow-up will usually be made via the responsible Monitor, although in exceptional circumstances the Global Drug Safety department may contact the Investigator directly to obtain further information or to discuss the event.

7.4.1.5 Safety Reporting to Health Authorities, Independent Ethics Committees/ Institutional Review Boards and Investigators

The Sponsor will send appropriate safety notifications to Health Authorities in accordance with applicable laws and regulations.

The Investigator must comply with any applicable center-specific requirements related to the reporting of SAEs (particular deaths) involving trial subjects to the IEC/IRB that approved the trial.

In accordance with ICH GCP, the Sponsor will inform the Investigator of "findings that could adversely affect the safety of subjects, impact the conduct of the trial or alter the IEC's/IRB's approval/favorable opinion to continue the trial". In particular, and in line with respective regulations, the Sponsor will inform the Investigator of AEs that are both serious and unexpected and are considered to be related to the administered product (suspected unexpected serious adverse reactions [SUSARs]). The Investigator should place copies of Safety reports in the Investigator Site File. National regulations with regard to Safety report notifications to Investigators will be taken into account.

When specifically required by regulations and guidelines, the Sponsor will provide appropriate Safety Reports directly to the concerned lead IEC/IRB and will maintain records of these notifications. When direct reporting is not clearly defined by national or center-specific regulations, the Investigator will be responsible for promptly notifying the concerned IEC/IRB of any Safety Reports provided by the Sponsor and of filing copies of all related correspondence in the Investigator Site File.

7.4.1.6 Monitoring of Subjects with Adverse Events

Any AEs are recorded and assessed continuously throughout the trial (see Section 7.4.1.3) and are assessed for final outcome at the Safety Follow-up visit. All SAEs ongoing at the Safety Follow-up visit must be monitored and followed up by the Investigator until stabilization or until the outcome is known, unless the subject is documented as "lost to follow-up". Reasonable attempts to obtain this information must be made and documented. It is also the responsibility of the Investigator to ensure that any necessary additional therapeutic measures and follow-up procedures are performed.

7.4.2 Pregnancy and In Utero Drug Exposure

Only pregnancies considered by the Investigator to be related to trial treatment (for example, resulting from a drug interaction with a contraceptive medication) are considered to be AEs. However, all pregnancies with an estimated conception date during the period defined in Section 7.4.1.3 must be recorded by convention in the AE page/section of the eCRF. The same rule applies to pregnancies in female subjects and to pregnancies in female partners of male subjects. The Investigator must notify the Sponsor/designee in an expedited manner (within a maximum of 24 HOURS after becoming aware of the event) of any pregnancy using the Pregnancy Report Form, which must be transmitted according to the same process as described for SAE reporting in Section 7.4.1.4.

Investigators must actively follow up, document and report on the outcome of all these pregnancies, even if the subjects are withdrawn from the trial.

The Investigator must notify the Sponsor/designee of these outcomes using the Pregnancy Report Form. If an abnormal outcome occurs, the SAE Report Form will be used if the subject sustains an event and the Parent-Child/Fetus Adverse Event Report Form if the child/fetus sustains an event.

Any abnormal outcome must be reported in an expedited manner as described in Section 7.4.1.4, while normal outcomes must be reported within 45 days after delivery.

In the event of a pregnancy in a subject occurring during the course of the trial, the subject must be discontinued from trial medication immediately. The Sponsor/designee must be notified without delay and the subject must be followed as mentioned above.

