Tumor assessment: Tumor assessment will be performed according to RECIST version 1.1. The baseline tumor assessment is to be performed during the screening period within 28 days before the start of trial treatment. Computed tomography (CT) or magnetic resonance imaging (MRI) with contrast enhancement is recommended for tumor assessment. Subsequent tumor response evaluations will be assessed every 6 weeks (± 3 days) starting from the randomization day until occurrence of PD regardless of any cycle delay. If treatment is discontinued for reasons other than PD, subjects will continue to have tumor assessments until either PD, the start of a new antitumor treatment, death, the termination of the trial, or loss of follow up, whichever comes first. If symptoms are suggestive of PD, subjects will be evaluated by imaging studies thereafter for documentation and confirmation of the tumor responses. The details of documentation of tumor assessment is described in Section 7.3.1.

Safety follow-up period: All subjects in Arm A and B will be followed up continuously for safety evaluations according to schedule of assessments in Table 1.1 starting from date of first signature of informed consent. A Safety Follow-up visit will be performed 30 days (± 3 days) after the last dose of trial treatment or immediately before starting any new antitumor treatment. During the treatment period, additional safety evaluations will be on a weekly basis (Arm A only) for physical examination, vital signs, documentation of AEs and concomitant medications, and also at the start of each cycle (for both arms) for ECOG performance status, ECG, hematology, biochemistry and urinalysis. Survival data and any information on new antitumor treatments will be collected every 3 months after the EOEA visit until either death, loss of follow up, or the termination of the trial, whichever comes first.

Primary and secondary endpoints: The primary endpoint of this trial is PFS time, as assessed by an IRC. Secondary endpoints include PFS time, as assessed by the Investigator, OS time, BOR rate, DCR, duration of response, and safety (see Section 8).

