5.3.1 Inclusion Criteria

For inclusion in the trial, subjects should fulfill all of the following inclusion criteria:

- 1. \geq 18 years of age.
- 2. Histologically and/or cytologically confirmed diagnosis of SCCHN.
- 3. Recurrent and/or metastatic SCCHN, not suitable for local-regional treatment. Subjects with recurrent disease only (no metastases) must have received prior radiotherapy (as adjuvant treatment after surgery or as treatment for locally advanced SCCHN) as part of "loco-regional treatment", and the radiotherapy and the radiotherapy must have been completed more than 6 months before screening imaging.
- 4. Presence of at least 1 measurable lesion according to RECIST version 1.1.
- 5. Signed written informed consent before any trial-related activities are carried out.
- 6. ECOG performance status of 0 or 1.
- 7. Neutrophils $\ge 1.5 \times 10^9$ /L, platelet count $\ge 100 \times 10^9$ /L, and hemoglobin ≥ 90 g/L.
- 8. Total bilirubin $\le 2 \times$ upper limit of normality (ULN); aspartate aminotransferase (AST) and alanine aminotransferase (ALT) $\le 3 \times$ ULN (if liver metastasis exists, ALT and AST $\le 5 \times$ ULN).
- 9. Serum corrected calcium, potassium and magnesium corrected within normal range (electrolyte correction is permitted during screening).
- 10. Creatinine clearance ≥60 mL/minute (24 hours creatinine clearance might be requested by the Investigator for confirmation, if calculated creatinine clearance is <60 mL/min).

11. Effective contraception if procreative potential exists (applicable for both male and female subjects) until at least 3 months after the last dose of trial treatment.

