- 16. Past or current history of neoplasm other than SCCHN, except for curatively treated nonmelanoma skin cancer, in situ carcinoma of the cervix, or other cancer curatively treated and with no evidence of disease for at least 5 years.
- 17. Any investigational medication within 30 days before randomization.
- 18. Female subjects who are pregnant (absence to be confirmed by serum β-human chorionic gonadotropin [HCG] test) or breast feeding, or males and females of reproductive potential not willing or not able to employ a highly effective method of birth control/contraception to prevent pregnancy from 2 weeks before receiving trial treatment until 3 months after receiving the last dose of trial treatment. A highly effective method of contraception is defined as having a low failure rate (< 1% per year) when used consistently and correctly.
- 19. Concurrent treatment with a prohibited medication (see Section 6.5.2).
- 20. Subjects with any concurrent medical condition or disease that will potentially compromise the conduct of the trial at the discretion of the Investigator.
- 21. Legal incapacity or limited legal capacity.

Subjects must fulfill all eligibility criteria to be enrolled in this trial. No exemption from any inclusion and exclusion criteria will be allowed. If any deviation from eligibility is retrospectively detected for an already enrolled subject, the Investigator and Sponsor must decide immediately whether it is safe to treat this subject further within the trial (see Section 5.4.2).

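### eCRF recording of pregnancies ends about 30 days after the last dose, although contraception is required for 3 months, and Section 7.4.2 does not say whether notification and outcome follow-up share that limit

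*Protocol*

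**What the plan says.** Protocol Section 7.4.2 sets four duties:

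- **Recording.** It states that "all pregnancies with an estimated conception date during the period defined in Section 7.4.1.3 must be recorded by convention", on the AE page of the eCRF. The rule applies to female subjects and to female partners of male subjects.
- **Notification.** Within 24 hours of learning of it, the investigator must inform the sponsor "of any pregnancy using the Pregnancy Report Form". This sentence names no conception period.
- **Outcome follow-up.** Outcomes must be pursued and reported, even after a subject has withdrawn. The pregnancies meant are identified only by a reference back to the preceding text.
- **Pregnancy in a subject.** A last paragraph, opening "In the event of a pregnancy in a subject occurring during the course of the trial", requires prompt notification and follow-up. It does not mention partners.

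The period that governs recording is defined in Section 7.4.1.3. It starts at the first signature of informed consent and "continues until the Safety Follow-up visit". Section 5.1 fixes that visit: "Safety Follow-up visit will be performed 30 days (± 3 days) after the last dose of trial treatment" "or immediately before starting any new antitumor treatment".

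The contraception requirement runs longer. Inclusion criterion 11 asks for it "until at least 3 months after the last dose of trial treatment". Exclusion criterion 18 rules out men and women of reproductive potential who will not or cannot "prevent pregnancy from 2 weeks before receiving trial treatment until 3 months after receiving the last dose of trial treatment". Sections 6.5.1 and 7.2.5 instead require contraception for the duration of the trial.

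Section 7.1.7 lists what is asked at the 3-monthly survival contact: survival status, later antitumor treatment, outcome of skin reactions, and resolution of ongoing SAEs. Pregnancy is not listed.

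**The concern.** The protocol asks subjects of both sexes to avoid conception for 3 months after the last dose, yet its explicit rule for recording conceptions closes after about 1 month. The wording around that rule does not settle whether the shorter limit also governs the 24-hour notice and the outcome follow-up. A site could reasonably read it either way.

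At stake is safety information. A conception in the second or third month after the last dose, in a subject or a partner, might not be entered in the eCRF, and its outcome might not be pursued. Such an outcome may not be recoverable later. Detection is a second weakness: once efficacy visits end, nothing in the listed survival contact prompts a site to ask.

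**Working it through.** The documents give no figure for the coverage of pregnancy reporting, so there is none to reproduce. The check compares two windows, both counted from the last dose.

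**Inputs**
- Length of the post-dose contraception requirement, W: 3 months (Protocol 5.3.1 and 5.3.2).
- Days per month: 30.4375 (SAP Section 11, conversion factors).
- Day of the Safety Follow-up visit, V: 30, with a window of 27 to 33 (Protocol 5.1), or earlier if new antitumor treatment starts.

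**Formula**

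Uncovered share = (W − V) / W, with W = 3 × 30.4375 = 91.3 days.

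**Results**

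| Visit day V | Days outside recording window | Share of 91.3 days |
|---|---|---|
| 33 | 58.3 | 63.9% |
| 30 | 61.3 | 67.1% |
| 27 | 64.3 | 70.4% |
| 14 (assumed early start of new treatment) | 77.3 | 84.7% |
| 7 (assumed early start of new treatment) | 84.3 | 92.3% |

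Taking 3 months as 90 or 92 days moves the on-schedule range only to 63.3% to 70.7%.

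**Do other provisions cover the remaining days?**
- The 24-hour notice has no stated window, but it depends on the investigator becoming aware, and it directly follows the windowed rule.
- The paragraph on a pregnancy during the trial reaches into survival follow-up, but only for subjects.
- Section 7.4.1.3 puts no time limit on SAEs related to cetuximab, and Section 7.4.1.1 counts a congenital anomaly as an SAE. That helps only if the event is attributed to cetuximab. The rule does not name cisplatin, carboplatin or 5-FU.
- Subjects who stop treatment without progression keep 6-weekly visits with AE documentation (Section 7.1.4) until the EOEA visit. Subjects whose EOEA visit has already taken place do not.
- The AE row of Table 1.1 appears to extend to the survival follow-up column, although the table is hard to read in the available text. The list in Section 7.1.7 is narrower.
- After the OS cut-off, Section 7.1 restricts reporting to SAEs during treatment and at the EOEA visit.

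Each provision covers part of the gap. None sets a window for partners, or an active question, that runs to the end of the contraception period.

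**The case against.** The strongest reply is that the limited sentence concerns an eCRF entry made by convention, while the duty that matters for safety is the 24-hour notice, which is unrestricted as written. A pregnancy in a subject during the trial is also notifiable and followed, and the trial continues through survival follow-up. On that reading a late conception known to the site still reaches the sponsor. This stands to the extent that the text cannot be said to exempt late conceptions from reporting. It does not remove the ambiguity about outcome follow-up, the omission of partners from the last paragraph, or the lack of a question that would bring a case to light.

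A second reply is that late conception need not mean exposure. Section 3.7.1 gives a mean cetuximab half-life of 112 hours (range 63 to 230). On simple first-order decay, the fraction left at day 30 (720 hours) is 2^(−720/112), about 1%, and 2^(−720/230), about 11%, at the longest half-life. The protocol gives no half-life for the chemotherapy drugs. This also stands: exposure after day 30 is not demonstrated. The point rests on the protocol's own contraception period, not on a claim about drug levels.

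A third reply concerns the denominator. Exclusion criterion 18 starts 2 weeks before treatment and includes treatment itself. Assume six on-time cycles, with the last 5-FU day at 5 × 21 + 5 = 110. The whole window is then about 14 + 110 + 91 = 215 days, and 61 uncovered days are about 28% of it. That is correct, so the 67% must be stated as a share of the post-dose part only.

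**Conclusion.** The mismatch holds. The eCRF recording window for pregnancies closes at the Safety Follow-up visit, while contraception is required until 3 months after the last dose. For a visit on schedule, 64% to 70% of the post-dose days fall outside the recording window (67% at day 30), and more if the visit is brought forward. Whether notification and outcome follow-up share that limit is not stated.

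A reader might infer three stronger things, none of which the documents support:
- That conceptions after the visit need not be reported or followed at all. The notification sentence has no conception window, so the defect is an unclear scope rather than an exclusion.
- That two thirds of the entire contraception period is uncovered. The pre-treatment and treatment parts fall largely or wholly within the existing window, which opens at consent.
- That in utero exposure is shown for these conceptions. The documents state a contraception requirement, not a period of proven risk.

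The result assumes 30.4375 days per month. That few pregnancies will occur is an expectation, since the documents give no rate. The point concerns safety capture only; no efficacy analysis depends on it. It is worth correcting because a stated rule is too short for the protocol's own requirement.

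**What to change.** Reconcile Protocol Sections 5.3.1, 5.3.2, 7.4.1.3 and 7.4.2. State one conception window that applies to eCRF recording, 24-hour notification and outcome follow-up alike, for subjects and for partners. Keep the present start at informed consent, and end the window no earlier than the contraception period the protocol states. A start at first dose should be avoided: it would drop the present cover during screening, which can last 28 days and takes in the pre-treatment weeks named in exclusion criterion 18. Sections 6.5.1 and 7.2.5 describe the contraception period differently and should be brought into line at the same time.

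Add a question on pregnancy in the subject or a partner to the existing 3-monthly contact in Section 7.1.7.

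The cost is a short protocol amendment, a small change to the survival follow-up eCRF page, and one question at a contact already planned. The Pregnancy Report Form already exists. One limitation remains: the contact may be with family or a referring doctor, who may be poorly placed to answer about a partner's pregnancy.
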